3.2 General Design AD Sub-Study

Briefly, after randomization to treatment with TMS+CILT or sham TMS+CILT, all subjects will undergo baseline behavioral testing, neuroimaging, and genetic testing before receiving 10 treatment sessions over 2 weeks. Immediate post-treatment effects will be assessed within 4 days of the completion of therapy by repeating the baseline probes of treated and untreated stimulus sets from CILT. At 6 and 12 weeks after the completion of TMS, subjects will return for follow-up assessments during which the same tasks administered in Visits 1 and 2 will be

repeated. Subjects who are able to undergo MRI scanning will have anatomic and fMRI scans at T3 and T17. Subjects who are not able or willing to undergo MRI will undergo CAT scan of the head.

3.2.1 Baseline Phase

The baseline phase will consist of 3 sessions, each lasting 1-2 hours depending on the stamina of the subject. The point of the baseline testing is to characterize the subject's language function. To that end, a number of standard language and neuropsychological tasks will be administered. These include the Western Aphasia Battery (121), Pyramids and Palm Trees test (52), Figural Fluency Test (108), word and non-word repetition tasks, the Nicholas and Brookshire Narratives (88), CILT stimulus naming, and Northwestern Assessment of Verbs and Sentences (see below for details), and the *Repeatable Battery for the Assessment of Neuropsychological Status* (147). Additionally, during the baseline, subjects will undergo an MRI of the brain or, if they have a contraindication to MRI, a CAT scan of the head. No contrast will be used. If they consent to DNA sampling, participants will also have a saliva sample taken for the purpose of genotyping.

All assessments listed are not mandatory. If the participant wishes to discontinue testing or refuses to perform a certain test due to frustration or fatigue, their request will be granted and not considered a deviation. Instead we will make note of any refused tests in our case report form (i.e. visit checklist).

3.2.2 Study Intervention Phase

In the treatment phase, there will be 10 TMS sessions over 2 consecutive weeks. We will employ repetitive TMS (rTMS) in which 30 two second trains of 10 Hz TMS will be delivered every 30 seconds to the left inferior pars triangularis and to the left posterior superior temporal gyrus, both at 100% MT. There will be a total of 600 pulses (30 trains x 2 seconds at 10 Hz) to each site in each session for a total of 1200 pulses/session. Each rTMS treatment session will be immediately followed by a 60-minute session of SLT.

3.2.3 Follow Up Phase

There will be two 6-week post-treatment visits and two 12-week post-treatment visits in which the full battery of language and cognitive assessments will be repeated. Subjects who are able to undergo MRI scanning will have anatomic and fMRI scans at or after the 12-week post-treatment visit.

All assessments listed are not mandatory. If the participant wishes to discontinue testing or refuses to perform a certain test due to frustration or fatigue, their request will be granted and not considered a deviation. Instead we will make note of any refused tests in our case report form (i.e. visit checklist).

3.2.4 Allocation to Interventional Group

Participants will be randomized to either TMS or sham TMS in a 2:1 allocation ratio using permuted blocks of variable size. The unblinded study coordinator will be responsible for generating the random numbers used to conduct the randomization.

3.3 Study Endpoints

3.3.1 Primary Study Endpoints

The primary endpoint will be overall change in WAB-AQ between the first baseline visit and the 6 month follow-up visit

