3.1 General Design

The overall timeline for each subject's participation is indicated in Figure 1. Briefly, after randomization to treatment with TMS+CILT or sham TMS+CILT, all subjects will undergo baseline behavioral testing, neuroimaging, and genetic testing before receiving 10 treatment sessions over 2 weeks. Immediate post-treatment effects will be assessed within 4 days of the completion of therapy by repeating the baseline probes of treated and untreated stimulus sets from CILT. At 3 and 6 months after the completion of TMS, subjects will return for follow-up assessments during which the same tasks administered in Visits 1 and 2 will be repeated. Subjects who are able to undergo MRI scanning will have anatomic and fMRI scans at T5 and T22. Subjects who are not able or willing to undergo MRI will undergo CAT scan of the head.

Figure 1: Timeline for each subject

Screening Visit	Baseline 1	Baseline 2	Baseline 3	Baseline 4	Treatment 1-10	Follow-up 1	Follow-up 2 & 3	Follow-up 4, 5, 6
Visit 1	Visit 2	Visit 3	Visit 4	Visit 5	Visit 6-16	Visit 17	Visit 18-19	Visit 20-22
-Informed Consent	-WAB	-WAB	-Leftover Testing	-MRI/CAT scan	Real or Sham TMS (20 min, 1hz at 90% MT) + CILT	-CILT probe	3-months: -same as Baseline 1 & 2	6-months: -same as Baseline 1 & 2 -MRI scan
-Inclusion/Exclusion Criteria	-PNT	-Ruff Figural Pyramids and Fluency Test	-Baseline will continue into 4th and 5th visits if necessary					
-Demographics History	-Pyramids and Palm Trees	-Word and non-word repetition						
-Medical History	-Communication Confidence	-Cinderella Story						
-Medical Intake								
-Geriatric Depression Scale	Scale	-CILT baseline						
120 minutes	120-180 minutes	120-180 minutes	60-180 minutes	120 minutes	90-120 minutes	60 minutes	120-180 minutes	120-180 minutes

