3.1.1 Baseline Phase

The baseline phase will consist of 3 sessions, each lasting 1-2 hours depending on the stamina of the subject. The point of the baseline testing is to characterize the subject's language function. To that end, a number of standard language and neuropsychological tasks will be

administered. These include the Western Aphasia Battery (121), Pyramids and Palm Trees test (52), Figural Fluency Test (108), word and non-word repetition tasks, the Nicholas and Brookshire Narratives (88), CILT stimulus naming, and Northwestern Assessment of Verbs and Sentences (see below for details), as well as a measure of grip strength and finger flexibility. Additionally, during the baseline, subjects will undergo MRI of the brain or, if they have a contraindication to MRI, a CAT scan of the head. No contrast will be used. If they consent to DNA sampling, participants will also have a saliva sample taken for the purpose of genotyping.

All assessments listed are not mandatory. If the participant wishes to discontinue testing or refuses to perform a certain test due to frustration or fatigue, their request will be granted and not considered a deviation. Instead we will make note of any refused tests in our case report form (i.e. visit checklist).

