7.5 Other Evaluations, Measures

The following battery of language and cognitive tasks will be administered prior to TMS and at 3 and 6 months after the completion of TMS: (1) The *Western Aphasia Battery* (WAB: 121) samples a number of different language functions and generates a summary score between 0-100 (Aphasia Quotient, AQ), interpretable as general aphasia severity. The WAB will be administered on two occasions prior to treatment to obtain a stable baseline. (2) The *Philadelphia Naming Test* (PNT) is a 175-item test of common object (picture) naming designed to measure retrieval of known words. Computational models have been developed that relate an individual's performance on the PNT (accuracy and error breakdown) to the integrity of semantic and phonological stages of naming (38, 136), thus producing a psycholinguistic diagnosis of the word production impairment. (3) Word and non-word repetition tests from the *Moss Psycholinguistic Aphasia Database* (MAPPD; 77) will be used to further assess lexical and post-lexical phonological encoding (31, 89). Word repetition will also be used to quantify instances of consonant distortion, prosodic alteration, and other features of speech apraxia (e.g., 105, 115). (4) The Pyramids and Palm Trees test (Picture version; 52) will be used to assess core semantic memory. (5) The *Communication Confidence Rating Scale for Aphasia* (144) will be administered to assess changes in quality of communication in daily life. (6) Narrative discourse as an indicator of functional communication will be assessed with the *Cinderella* story (145, 146). (7) Finally, 2 pre-treatment baselines will be obtained on the stimuli used for CILT. We note that the baseline sessions (T1 and T2, Figure 2) may require more than one day to complete; the entire series of baseline sessions (T1, T2 and T3) will be completed in 2 weeks or less.

One might speculate that improvements in language associated with TMS to the right IFG would be associated with adverse effects in other domains. We found no evidence of this in our previous work, nor are we aware of reports of such a phenomenon. To address this possibility, we will administer the Ruff Figural Fluency Test (108), which has been shown to be sensitive to dysfunction of the right prefrontal cortex.

While there has been research on the effects of TMS on motor recovery for patients with stroke-induced hemiparesis, we do not expect our stimulation location to have an effect on

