8.1 Primary Endpoint

The primary endpoint will be overall change in WAB-AQ between the first baseline visit and the 6 month follow-up visit

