8.3 Sample Size and Power Determination

To calculate power, we started from an ambitious but realistic estimate of the population available at the participating recruitment sites. We intend to recruit up to 83 subjects to achieve a post-attrition sample size of 75. This attrition estimate is based on past experience. In previous treatment studies involving TMS (e.g., 76) and tDCS (119) we have had very low attrition; we attribute this to the fact that PWA are often very motivated by the opportunity to participate in a study with potential benefit.

Subjects (or will be allocated to TMS and CILT and sham TMS and CILT in a 2:1 ratio. Assuming a type I error rate of $\alpha=0.05$, we will have 80% power to detect a difference in mean change of 0.7 standard deviation units based on a two-sample t-test at 6 months. A 2:1 ratio was selected to provide more information about outcomes among patients randomized to TMS+CILT and as an incentive to recruitment since prospective participants are more likely to enroll in sham-controlled trials when the probability of receiving active treatment is greater. Efficiency loss associated with unequal allocation is minimal, amounting to an additional 6 participants required relative to 1:1 randomization for our design. Maher et al. (unpublished) report a standard deviation of change in the WAB AQ of 5.7 points in groups treated with Constraint Induced Language Therapy (see below). Assuming that our patients are similar, we are powered to detect a difference of 4 points in mean change in the WAB AQ between TMS+CILT and sham TMS+CILT arms. Note that our assumed effect size of 0.7 is conservative; Ren et al. (103) reported a Standard Difference of Means (a measure of effect size) of 1.26 for the general measure of severity of impairment (e.g., BDAE, Aachen Aphasia Test) based on a meta-analysis of 5 trials including a total of 96 subjects in which rTMS was compared to sham rTMS. The statistical analyses employ methods for longitudinal data in which 3 and 6 month assessments are considered simultaneously, thereby providing additional power to detect smaller effects.

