8.4 Statistical Methods

8.4.1 Statistical Analysis of Primary Outcomes

Prior to analysis, the presence of outliers will be determined by examining descriptive statistics and graphical summaries of primary and secondary outcomes. As noted, the primary end-point will be the change in WAB AQ from the baseline for the treatment and sham groups. An intent-to-treat analysis will be performed using Linear Mixed Models for repeated-measures outcomes using outcomes at 3 and 6 months simultaneously. LMM is a regression-based approach that is suitable for repeated assessments, unlike generalized linear model regression. Additionally, unlike ANOVA, it is robust to missing data under the missing at random (MAR) assumption and sphericity assumptions. The primary outcome model will include change from baseline on the WAB AQ as the response and intervention, assessment end-point, and the interaction of intervention and end-point as fixed effects. The model will also include the baseline WAB AQ score as a predictor to increase efficiency and account for baseline imbalances in aphasia severity. A random intercept and end-point slope will be included to reflect between-subject heterogeneity in changes in WAB AQ scores. To examine possible bias in estimated intervention effects due to data missing not at random, sensitivity analyses, such as shared parameter and pattern mixture models, will be used. Secondary analyses will adjust for covariates that are imbalanced between intervention arms as well as demographic and clinical variables such as age, history of depression, lesion size, aphasia type, gender, and aphasia severity. In an exploratory analysis, we will evaluate whether there is a direct treatment effect on the WAB AQ that is not mediated by changes in response to CILT stimuli by further adjusting our primary outcome model for changes in CILT stimuli (67).

The statistical modeling of the secondary outcome (PNT) will involve similar analyses, but with items and participants modeled as random effects. Item-level response types will be analyzed separately (e.g., correct vs. incorrect; semantic error versus other response, etc.) to allow for determination of intervention effects specific to response type.

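### The primary endpoint is anchored to the first of two pre-treatment WABs; the second has no stated role, so precision already collected goes unused

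*Combined protocol and SAP*

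**What the plan says.** Section 3.3.1 defines the primary endpoint as "overall change in WAB-AQ between the first baseline visit and the 6 month follow-up visit", and Section 8.1 repeats this word for word. Sections 6.3.1 and 6.3.3 list the WAB at both Baseline 1 and Baseline 2. Section 7.5 gives the reason: "The WAB will be administered on two occasions prior to treatment to obtain a stable baseline". It also limits the interval: "the entire series of baseline sessions (T1, T2 and T3) will be completed in 2 weeks or less".

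The primary model in Section 8.4.1 takes change from baseline as the response and adds a baseline term: "The model will also include the baseline WAB AQ score as a predictor to increase efficiency". It does not say whether baseline there is the first score, the second or their mean. Section 8.3 bases power on a "standard deviation of change in the WAB AQ of 5.7 points", a 4-point difference, 2:1 allocation of 75 evaluable subjects and a two-sample t-test at 6 months.

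Two further statements bear on a remedy. Section 3.1 puts randomization first but says that "all subjects will undergo baseline behavioral testing, neuroimaging, and genetic testing before receiving 10 treatment sessions over 2 weeks". Section 3.1.1 says of the test battery: "All assessments listed are not mandatory".

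**The concern.** The plan has a stated purpose for the second WAB, and its endpoint definition ignores that purpose. Measurement error in the first WAB is subtracted from every follow-up score, so it inflates the variance of the change at 3 and at 6 months alike. Modelling the two time points jointly does not remove it, because both changes share the same baseline error. Averaging two pre-treatment scores halves that error variance if the errors are independent, and cuts it by a quarter if they correlate at 0.5.

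There is also a question of definition. With baseline undefined in Section 8.4.1, an analyst could take the first score, the second or the mean. That choice should be closed before anyone sees results by arm.

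**Working it through.** **Inputs from the documents (Section 8.3):** SD of change 5.7, difference 4, 75 evaluable subjects at 2:1 (50 and 25), alpha 0.05. Sidedness is not stated; two-sided is assumed.

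**Assumptions, not in the documents:** the error SD of one WAB, *e*, is 1.5 to 3 points; the errors of the two baselines correlate at *r* = 0 or 0.5; the 5.7 comes from single pre and post scores.

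**Step 1: the plan's own figure.** Noncentrality = (4/5.7)/√(1/50 + 1/25) = 2.865 on 73 degrees of freedom. The exact two-sided t-test gives power 80.7% (80.5% for exactly 0.7 SD). The stated 80% reproduces.

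**Step 2: mean of two baselines.** The single baseline's error variance e² is replaced by e²(1 + r)/2, so

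Var(change) = 5.7² − e² + e²(1 + r)/2 = 32.49 − e²(1 − r)/2.

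Equivalent extra subjects = 75 × (32.49/Var − 1). For example, e = 3 and r = 0 gives Var = 32.49 − 4.5 = 27.99, SD 5.29, and 75 × (32.49/27.99 − 1) = 12.1.

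| e | r = 0: SD | power | extra subjects | r = 0.5: SD | power | extra subjects |
|---|---|---|---|---|---|---|
| 1.5 | 5.60 | 82.1% | 2.7 | 5.65 | 81.4% | 1.3 |
| 2.0 | 5.52 | 83.1% | 4.9 | 5.61 | 81.9% | 2.4 |
| 2.5 | 5.42 | 84.5% | 8.0 | 5.56 | 82.6% | 3.8 |
| 3.0 | 5.29 | 86.1% | 12.1 | 5.50 | 83.4% | 5.6 |

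**Step 3: second WAB missing in 20% (assumed).** Var = 0.8 × Var(mean) + 0.2 × 32.49. Power is 81.8–85.0% for r = 0 and 81.2–82.9% for r = 0.5.

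**Step 4: does the planned covariate already do this?** Let s be the true between-subject SD of baseline AQ (assumed 15 to 20 points), with r = 0 and true change unrelated to true baseline. The residual variances are:

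- First WAB for both change and covariate: 32.49 − e⁴/(s² + e²). Power 80.7–81.1%.
- Change from the first WAB, mean as covariate only: 32.49 − (e²/2)²/(s² + e²/2). Power 80.7–80.8%.
- Mean for both: 32.49 − e²/2 − (e²/2)²/(s² + e²/2). Power 82.1–86.2%.

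At s = 15 and e = 3 the three variances are 32.14, 32.40 and 27.90. Lowering s to 10 raises the first option only to 81.6% at e = 3. The gain comes from changing the change score; the covariate alone does not recover it.

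**Step 5: could averaging hurt?** If the second WAB's error variance is k times the first's, the mean is better while (1 + k + 2r√k)/4 < 1. That holds for k below 3 at r = 0 and below 1.7 at r = 0.5. A practice effect common to both arms cancels in the between-arm comparison.

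**The case against.** The strongest reply is that a first-visit baseline is explicit, pre-specified, identical in both places that define it, and valid. There is no bias and no power shortfall, so this is a refinement. That is right as far as it goes, and it limits the weight of the point.

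The gain may also be smaller than the table shows. At e = 1, power is 81.3% (r = 0) or 81.0% (r = 0.5), worth about one subject. At r = 0.75 with e from 1.5 to 3 it is 81.0–82.1%, or 0.7 to 2.7 subjects. Both baselines fall within two weeks while the outcome is six months away, so slow fluctuation shared by the two tests cannot be excluded. The 12-subject figure needs the largest assumed error, full independence and no missing scores. The calculation also uses the plan's t-test at 6 months and not the mixed model. All of this stands, but it shrinks the gain without making averaging harmful.

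A second reply is that Section 7.5 does not mention averaging; the repeat might be a stability check or familiarisation. The text does not rule that out, but neither does it give any rule for using the second score in that way.

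A third is that optional testing would mix one-score and two-score baselines, with precision perhaps varying with severity. That is a fair caution; Step 3 allows only for a uniform 20%. Finally, the follow-up visits repeat the battery of Visits 1 and 2, which lists the WAB twice, so it is also unclear which 6-month score counts. That is a related gap that the same amendment should close.

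**Conclusion.** The concern holds. The endpoint names the first baseline visit only, and the second pre-treatment WAB has no stated part in it. The consequence is lost precision, neither bias between arms nor an underpowered trial. Under the stated assumptions the gain from averaging is about 1 to 5 percentage points of power, and less if the WAB's error is small or the two errors are strongly correlated. It also rests on the 5.7-point SD having come from single scores, which Section 8.3 does not say. If that SD already reflected averaged baselines, the first-visit endpoint would have less power than calculated in Step 1. The size is modest, but the data are already scheduled, so the change should be made.

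**What to change.** In Sections 3.3.1, 8.1 and 8.4.1, define baseline WAB AQ as the mean of the available pre-treatment WABs, or the single score where only one exists. Use it for both the change score and the covariate. Keep the first-visit baseline as a sensitivity analysis. State that the severity stratum recorded at randomization does not change. Say which 6-month WAB is used; if the WAB is in fact given twice at a follow-up, apply the same averaging rule there (no power figure is claimed for that).

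The cost is an amendment to the primary endpoint definition and one sentence in Section 8.4.1. The introduction to the AD sub-study describes the main trial as ongoing, so the amendment must be dated before unblinding. No visits or data are added. Baseline testing follows randomization, but both WABs precede the first TMS session, so treatment cannot affect the mean. Report how many baselines rest on one score, and record whether each WAB was done in person or by tele-assessment, since either mode is allowed.

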3.3.2 Secondary Study Endpoints

Change in naming accuracy on the PNT will serve as a secondary outcome measure

3.3.3 Primary Safety Endpoints

The risks from the behavioral tasks and imaging are minor. Data on adverse events occurring during the 2 weeks in which TMS is being administered will be collected by asking subjects at the beginning and end of every TMS session if they have noted any adverse effects or new symptoms since their most recent. Reports of adverse effects from TMS and other aspects of the study (brain imaging, behavioral tasks and CILT) will serve as the primary safety endpoint.

4 Study Population and Duration of Participation

4.1 Inclusion Criteria

Study subjects must meet all of the following inclusion criteria:

- Clinical evidence and MRI or CT verification of a single left hemisphere cerebral infarct, either ischemic and hemorrhagic, with moderate to severe aphasia as operationally defined by WAB-AQ scores between 85 and 20, inclusive. Patients will not be excluded on the basis of small (less than 1.5cm) lacunar strokes as these are extremely common in the population under study and for which the therapy is ultimately intended.
- Suffered their infarction at least 6 months prior to their testing.
- Be between the ages of 18 and 80.
- Must be able to understand the nature of the study, and give informed consent.

4.2 Exclusion Criteria

Study subjects must not meet any of the following exclusion criteria

- Multiple infarcts as defined by brain imaging
- History of serious and/or ongoing issues with substance abuse.
- Previous head trauma with loss of consciousness for more than 5 minutes
- Psychiatric illness (We note that subjects will be assessed with the 15-item Geriatric Depression scale. Because depression is very difficult to evaluate in aphasic subjects, potential subjects will not be excluded on the basis of the depression score, but this measure will serve as a covariate in subsequent analyses.)
- Chronic exposure to medications that might be expected to have lasting consequences for the central nervous system (e.g. haloperidol, dopaminergics).
- History of or neuropsychological findings suggestive of dementia

Additional contraindications related to TMS include:

- Uncontrolled seizures, as operationally defined by a history of seizure while taking their current medical regimen during the last 6 months.
- Previous brain surgery (excludes procedures where bone is removed to release pressure, such as a craniotomy, so long as the bone is replaced and allowed to fuse back together).
- Other medical or neurologic conditions, aside from stroke, in which the likelihood of developing a seizure is known to be increased.
- Other medical or neurologic conditions, in which a seizure would be particularly harmful (e.g., increased intracranial pressure)
- Presence of metallic hardware near coil; examples include cardiac pacemakers, intracardiac lines, intracranial stents, implantable defibrillators, medical pumps, ventriculo-peritoneal shunts, deep brain stimulators, and vagus nerve stimulators.
- History of tinnitus
- Pregnancy – there are no known problems in delivering TMS during pregnancy, but the issue has not been thoroughly addressed; all female participants must have a negative urine pregnancy test at the time of testing to participate

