4.4 AD Sub-Study Exclusion Criteria

Study subjects must not meet any of the following exclusion criteria:

- History of stroke
- History of seizure
- History of any other significant neurologic disease (e.g., ALS)
- Significant depression as defined by the Geriatric Depression Scale; subjects with scores suggesting significant depression will not be included and [name], Co-I and Neuropsychologist at the Penn Memory Center, will be available to address concerns regarding safety and provide a referral, if needed.
- Any significant medical disorder that, in the view of the investigators, could threaten the subject's ability to complete the study (e.g., cancer, significant cardiac disease)
- Any contraindications to TMS as specified in section 4.2 above

Additional contraindications related to MRI include the presence of any of the following devices:

1. Cardiac pacemaker
2. Other programmable implanted devices, e.g., for the carotid sinus, insulin pumps and nerve stimulators, lead wires or similar wires
3. Optic implant

4. Implanted cardiac defibrillator
5. Aneurysm clip
6. Any electronically, magnetically, and mechanically activated implant
7. Ferromagnetic implant: coils, filters, and stents; metal sutures or staples
8. Claustrophobia
9. Metal in eye or orbit
10. Tattooed eyeliner

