5.2.3 Stimulation Parameters

Our protocol involves repetitive TMS at a frequency of 1 Hz. According to established guidelines, the maximum safe duration of single trains of rTMS at 1 Hz using an intensity of 110% of MT is “>1800” (that is >30 minutes) (Wassermann, 1998). Working well within these guidelines, we will administer 1200 pulses in one session at 1 Hz (20 minutes) at 90% of MT. We note that recent evidence suggests that stimulation intensities as high as 120% of MT are safe in stroke patients, even when applied directly to the lesioned hemisphere (61) for a period of 10 days. Our protocol calls for stimulation at a relatively lower intensity (90% MT), applied to the undamaged hemisphere of the brain, which we feel increases the safety of the study. We also note that the stimulation parameters we propose were employed in our previous clinical trial employing rTMS (protocol #805362) in which we had no adverse events.

Prior to administering experimental TMS, we will determine the motor threshold (MT) of each patient by stimulating the motor cortex in the unaffected hemisphere. MT will be defined as the minimum percentage of machine output required to produce MEPs of at least 50 microVolts on at least 5 of 10 consecutive trials at the same location. MT will be determined by single-pulse stimulation of the motor cortex subserving the contralesional hand at a suprathreshold level and subsequently reducing the percentage of the machine output until MEPs are not identified. The coil will be placed with the handle pointing to the patient's back at about 45° from the vertical position. Following determination of MT, patients will undergo 1 Hz rTMS.

The sham TMS group will be treated in the same manner as the experimental group except that MT will not be determined for the sham group. Thus, subjects in this group will never receive TMS. Sham treatment will employ a sham coil that produces the same sound as the real coil. Additionally, surface electrodes will be placed on the scalp, which will simulate the sensation of TMS. The sham and real coils will be numbered and the coil used and the MT will be recorded for each session.

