6.1 Screening

The screening visit will consist of:

- Informed Consent
- Review of the Inclusion/Exclusion Criteria
- Review of Demographics/Medical History
- Medical Intake (performed by the study PI or [name], both of whom are neurologists).
- In cases where the baseline visits will be conducted via tele-assessment, the Ruff Figural Fluency test may be administered at this visit.

The anticipated time of this visit is 30 minutes; depending on the subject's interest and responses to the screening tests, this visit could be combined with Visit 1 below.

An initial remote screening visit may be conducted via Bluejeans. Before screening and the medical intake, remote consent will be obtained, with e-signatures collected via RedCAP (explained in detail below). An in-person Medical Intake screening may occur after the remote consent and screening.

At the time of screening, or sometime afterwards, the Aphasia Depression Rating Scale (ADRS) will be completed by the patient's caregiver. The caregiver rates the subject on 9 different items. The ADRS has high reliability, sensitivity and specificity and is specifically designed for evaluation of aphasic patients (147). The ADRS will be given to the patient's caregiver to complete at the

time of screening, or will be mailed to the caregiver or close relative before the baseline screening. The ADRS will serve as a covariate in statistical analysis.

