7.1 Medical Record Review

- Date of birth
- Address
- Contact information
- Hospital admission date and date of brain injury
- Past medical history as it relates to stroke and other neurologic conditions, cardiac status, and surgery
- Results of neuroimaging studies and dates, including MRI and/or CT exams
- Current and past medications or therapies

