12.1 Risks

12.1.1 Potential Risks

Potential risks of the behavioral and motor tasks are minimal and easily addressed (see below). The major risk associated with genetic testing is a loss of confidentiality.

There are well-known but rarely encountered risks from brain imaging with MRI and CT, or standard X-Ray exams. For the former, the risks include contrast administration (not relevant here), dislodging a metal object in the patient, interfering with an implanted device (e.g., pacemaker) and moving metallic objects in the scanner room. Protocols to deal with these issues are described below. The major risk from CT or X-rays is exposure to small amounts of ionizing radiation.

A variety of potential risks from repetitive TMS, including daily TMS administrations, have been identified (see 106 for a recent review); these include the following:

1. Seizures: Seizure induction represents the most serious known risk of TMS. The risk of seizures is quite low in subjects receiving single pulse TMS. Based on an extensive review of the literature, guidelines have been developed that specify the number of stimulations that may safely be given as a function of stimulus intensity (% of Motor Evoked Potential) and frequency of stimulation (138; see also Rossi et al, 2009). Using these guidelines there have been no published reports of seizures or evidence of after-discharge or spread of excitation in normal subjects receiving low-frequency repetitive TMS. We will adhere to the published guidelines.

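### The main-study seizure exclusion counts only seizures on the current regimen, so a recent seizure followed by a regimen change does not exclude

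*Combined protocol and SAP*

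**What the plan says.** All references are to the combined protocol and SAP.

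- **Section 4.2, first TMS contraindication:** "Uncontrolled seizures, as operationally defined by a history of seizure while taking their current medical regimen during the last 6 months".
- **Section 4.2, third TMS contraindication:** "Other medical or neurologic conditions, aside from stroke, in which the likelihood of developing a seizure is known to be increased".
- **Section 4.1:** the only waiting period in the inclusion criteria runs from the stroke: "Suffered their infarction at least 6 months prior to their testing".
- **Section 4.4, Alzheimer sub-study only:** "History of seizure" excludes, with no condition on regimen or time.
- **Section 6.1:** a neurologist carries out the medical intake. No seizure-free interval is stated there.
- **Section 7.1:** the record review covers neurologic history and "Current and past medications or therapies". It does not list the date of the last seizure or of the last regimen change.
- **Section 12.1.1:** "Seizure induction represents the most serious known risk of TMS".

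**The concern.** The 6-month window suggests that the authors wanted evidence of seizure control over time before stimulating. The condition on the current regimen removes that requirement where control is least established. A seizure is a natural reason to start or change treatment (clinical reasoning, not a figure from the documents), so the exception is not contrived. The rule also ranks candidates the wrong way round: someone on a stable regimen whose only seizure was just under 6 months ago is excluded, while someone whose seizure was a few weeks ago and whose treatment has just been changed is not.

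What is at stake is patient safety. Efficacy inference is not involved. The other safeguards (observation during stimulation, ending the session, a physician on call, stopping treatment after a seizure) act during or after an event. Eligibility is the main preventive control that depends on the candidate's own history.

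**Working it through.** The protocol gives no figure to reproduce here, and no power or sample-size calculation applies. The check applies the criterion as a rule and then looks for another rule that closes the gap.

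**Step 1. The rule.** As worded, a candidate is excluded if a seizure occurred (a) within the last 6 months and (b) while on the current regimen. Both must be true.

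**Step 2. Cases.** Dates are assumed for illustration.

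| Candidate | (a) | (b) | Result |
|---|---|---|---|
| Seizure 5 weeks before intake, regimen unchanged | yes | yes | excluded |
| Seizure just under 6 months before intake, regimen unchanged | yes | yes | excluded |
| Seizure 5 weeks before intake, regimen changed 4 weeks before, none since | yes | no | **not excluded** |
| As the line above, with a further seizure on the new regimen | yes | yes | excluded |
| As the third line, but a candidate for the Alzheimer sub-study | – | – | excluded under 4.4 |

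**Step 3. The other reading.** The 6-month phrase could instead describe how long the current regimen has been in force. The candidate in the third line has had no single regimen over that period, so the case is unresolved. The seizure still did not occur on the present regimen, and the wording still does not require exclusion.

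**Step 4. Other main-study criteria.**
- The third TMS contraindication sets stroke aside, so it does not clearly reach seizures caused by the stroke. If it did, it would exclude everyone with such a history, and the item on uncontrolled seizures would have little left to do.
- The fourth concerns conditions in which a seizure would be especially harmful. It does not address recent seizure history.
- Section 4.1 sets an interval from the infarct and none from the last seizure.
- Section 4.4 also lets investigators exclude for a significant medical disorder in their judgement. Section 4.2 has no equivalent clause.

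**Step 5. Size of the gap.** With an unchanged regimen, the required seizure-free time is 6 months (52 / 2 = 26 weeks). After a change with no seizure since, it can be anything from days up to 6 months. An active-arm subject receives 10 sessions × 1,200 pulses = 12,000 pulses over 2 weeks (section 3.1.2). That figure is exposure; it is not an estimate of seizure risk.

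**The case against.** The strongest reply is that the wording is deliberate. The item defines control on the treatment the subject takes now, and whether a regimen change restores control is a clinical judgement. That may have been the intention, but the protocol does not say so, and even then it sets no minimum time on the new regimen.

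Second, there are routes to exclusion. The list of TMS contraindications is introduced as if it were open-ended, an investigator could treat a recent seizure disorder as another neurologic condition, and a neurologist does the intake. All of this permits exclusion; none of it requires it, and the intake neurologist has no stated interval to apply.

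Third, the risk is probably low. Section 5.2.3 says: "Our protocol calls for stimulation at a relatively lower intensity (90% MT), applied to the undamaged hemisphere of the brain". It also reports no adverse events with the same parameters in the group's earlier trial. Section 12.1.1 cites over 250 subjects with aphasia, and a review of stroke hemiparesis studies (13 stimulating the lesioned hemisphere, 12 the other), without significant adverse effects. The stricter sub-study rule goes with stronger stimulation, 10 Hz at 100% of motor threshold. This stands, and it limits how serious the gap is. However, the documents do not say that any of those studies enrolled people with a recent seizure on a newly changed regimen, and the no-seizure statement tied to the safety guidelines concerns normal subjects.

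Fourth, the number affected is unknown. That also stands. In addition, baseline testing and imaging come before stimulation, so the seizure-free time at the first pulse is somewhat longer than at intake, though no minimum is stated.

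**Conclusion.** The concern holds. Under either reading of the 6-month phrase, a main-study candidate with a seizure in the last 6 months, a regimen change after it and none since is not required to be excluded, and no other main-study criterion requires it. For this subgroup, protection rests on clinical judgement at intake. The Alzheimer sub-study is unaffected.

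The conclusion rests on the wording alone. How many candidates it touches cannot be derived from the documents and may be small; the absolute risk is probably low. It should be corrected because the rule gives a perverse result on the hazard the protocol itself ranks highest, and the correction is cheap. Confidence is medium, mainly because the wording could reflect an unstated clinical decision.

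**What to change.** Reword the first TMS contraindication in 4.2 to exclude any seizure during the last 6 months, whether or not the medical regimen was changed afterwards. At the medical intake in 6.1, record the date of the last seizure and the date of the last regimen change.

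The 6-month window is the protocol's own; the clinical investigators should decide whether it is long enough. The cost is one eligibility line, two dates at a visit that already takes place, and possibly a few additional exclusions, whose number the documents do not allow one to estimate.
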